### **5.1.3 DOSE-LIMITING TOXICITIES**

Subjects in both dosing schedules will be evaluated for DLTs according to the National Cancer Institute-Common Terminology Criteria for Adverse Events ([NCI-CTCAE](#)), Version 4.03 during the 28-day period of Cycle 1 combination therapy. Intrasubject dose escalation to the RP3D may be permitted once that dose has been determined and after a discussion has occurred between the treating physician and **the Sponsor's** study medical monitor. The decision to escalate to the next higher dose of oprozomib in **this** study will be based on an assessment of study drug-related DLTs during Cycle 1 by the CSRC. The CSRC consists of investigators, the **Sponsor's** study medical monitor, and **the Sponsor's** drug safety representative. Each subject in the cohort under review will be discussed and assessed. Once all data have been presented, the CSRC will decide on the most appropriate course of action regarding dose escalation based on guidance in [Section 5.1](#).

Study drug is defined as the combination of oprozomib, pomalidomide, and dexamethasone. Study drug-related is defined as a reasonable likelihood of clinical causality based on time of event, biology, dechallenge improvement and that the AE was not likely explained by the subject's clinical state, underlying disease, concomitant medication, or study/nonstudy procedure. Definition of DLTs and additional details are provided in [Section 10.5](#).

### **5.1.4 SUBJECT REPLACEMENT**

Subjects must meet the following criteria to be considered evaluable for MTD determination during the 4-week DLT evaluation period unless a DLT occurs before the subject receives all planned doses of oprozomib for both the 5/14 and 2/7 dosing schedules:

- A minimum of 17 of 21 planned doses of pomalidomide must be received
- A minimum of 6 of 8 planned doses of dexamethasone must be received
- All planned doses of oprozomib must be received

Subjects not meeting all of the above criteria or assessed as unevaluable by the CSRC will be replaced.

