**Table 14 Guidelines for Dose Modification of Oprozomib/Placebo and Pomalidomide for Nonhematologic Toxicities**

Symptom	Findings	Recommended Action a	
		Oprozomib	Pomalidomide
Tumor Lysis Syndrome	Generally recognized in at least 3 or more of the following categories: (1) Increase in creatinine, uric acid, or phosphate of $\geq 50\%$ (2) Increase in potassium of $\geq 30\%$ (3) Decrease in calcium of $\geq 20\%$ , or (4) Increase in LDH $\geq 2$ -fold from baseline	Hold both oprozomib and pomalidomide until all abnormalities in serum chemistries have resolved to baseline; resume at full doses.	
Neuropathy	Grade 2 neuropathy with pain or $\geq$ Grade 3 neuropathy	Hold dose until toxicity resolves to $\leq$ Grade 1 or has returned to baseline. Resume study drug at 1 dose decrement.	Hold dose until toxicity resolves to $\leq$ Grade 1 or has returned to baseline. Resume study drug at 1 dose decrement from previous dose.
Infection	Grade 3 or 4	Hold both oprozomib and pomalidomide until systemic treatment for infection complete. If ANC $\geq 1.0 \times 10^9/L$ , resume both drugs at full dose. If ANC $< 1.0 \times 10^9/L$ , follow hematologic toxicities dose reduction guidelines (Table 13).	
Nausea, vomiting, diarrhea, or constipation	$\geq$ Grade 3 without optimal supportive care as defined by use of both a 5-HT 3 antagonist and aprepitant	Oprozomib-related: Full dose oprozomib but institute optimal supportive care.	Pomalidomide-related: Hold dose until toxicity resolves to $\leq$ Grade 1 or has returned to baseline. Resume study drug at 1 dose decrement from previous dose.
	$\geq$ Grade 3 with optimal supportive care as defined by use of both a 5-HT 3 antagonist and aprepitant	Oprozomib-related: Hold dose until toxicity resolves to $\leq$ Grade 1 or has returned to baseline. Resume study drug at 1 dose decrement.	
Fatigue	Grade 3 fatigue lasting $< 14$ days	Full dose.	Hold dose until toxicity resolves to $\leq$ Grade 1 or has returned to baseline. Resume study drug at 1 dose decrement from previous dose.
	Grade 3 fatigue lasting $\geq 14$ days	Hold dose until toxicity resolves to $\leq$ Grade 1 or has returned to baseline. Resume study drug at 1 dose decrement.	

Approved

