## 10.5 DEFINITION OF DOSE-LIMITING TOXICITY

During this study, assessment of DLTs will occur during the 28-day period of Cycle 1 combination therapy. For the purposes of this study, a DLT is defined as any of the study drug-related events listed below occurring within the 4 weeks after the first dose of combination therapy. Study drug-related is defined as a reasonable likelihood of clinical causality based on time of event, biology, dechallenge improvement and that the AE was not likely explained by the subject's clinical state, underlying disease, concomitant medication, or study/nonstudy procedure.

- Any toxicity requiring a dose reduction or requiring that a dose of oprozomib or pomalidomide be held in Cycle 1 that does not meet the criteria for DLT will be discussed by the CSRC to determine whether the subject should be considered evaluable for DLT determination. If it is determined that the subject is not evaluable for DLT, the subject will be replaced.
- A delay in ability to receive Day 1 dose of Cycle 2 due to a hematologic or nonhematologic drug-related toxicity persisting beyond 14 days from Cycle 1 Day 28 will be considered a DLT
- For a nonhematologic DLT, any  $\geq$  Grade 3 toxicity will be considered a DLT with exceptions as described below:
  - Grade 3 asymptomatic electrolyte abnormalities will not be considered a DLT
  - Asymptomatic Grade 3 hypophosphatemia lasting less than 24 hours will not be considered a DLT
  - Grade 3 nausea and vomiting will not be considered a DLT unless persisting longer than 3 days despite optimal supportive care, which at a minimum must include a 5-hydroxytryptamine type-3 (5-HT3) antagonist and aprepitant
  - Grade 3 diarrhea will not be considered a DLT unless persisting longer than 3 days despite optimal supportive care, which at a minimum must include loperamide (Imodium) and atropine diphenoxylate (Lomotil)
  - Grade 3 fatigue lasting < 14 days is not considered a DLT
  - $\geq$  Grade 3 hyperglycemia or toxicity attributed to dexamethasone is not considered a DLT (see dose reduction guidelines for dexamethasone in [Section 10.4.1](#))
  - $\geq$  Grade 3 rash attributed specifically to pomalidomide is not to be considered a DLT

Approved

CONFIDENTIAL

- Hematologic DLTs consist of the following:
  - Grade 4 neutropenia:
    - Absolute neutrophil count (ANC)  $< 0.5 \times 10^9/L$  lasting  $\geq 7$  days despite adequate growth factor support (eg, G-CSF)

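### The exemption in Protocol 5.1.4 is too narrow: a subject with complete oprozomib intake, a pomalidomide or dexamethasone shortfall and a late DLT becomes unevaluable for the MTD and is replaced

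*Protocol*

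**What the plan says.** Protocol 5.1.4 (Subject Replacement), with the same text in the synopsis, lists three conditions for being evaluable for MTD determination:

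- Pomalidomide: "A minimum of 17 of 21 planned doses of pomalidomide must be received".
- Dexamethasone: at least 6 of the 8 scheduled doses.
- Oprozomib: "All planned doses of oprozomib must be received".

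The only exemption is introduced by "unless a DLT occurs before the subject receives all planned doses of oprozomib for both the 5/14 and 2/7 dosing schedules". The consequence of failing is mandatory: "Subjects not meeting all of the above criteria or assessed as unevaluable by the CSRC will be replaced".

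Section 10.5 defines a DLT as a listed drug-related event "occurring within the 4 weeks after the first dose of combination therapy". It adds a further type, a delay of Cycle 2 Day 1 caused by drug-related toxicity "persisting beyond 14 days from Cycle 1 Day 28 will be considered a DLT".

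Under Section 5 the last oprozomib day is Day 19 on the 5/14 schedule and Day 23 on the 2/7 schedule. Pomalidomide runs to Day 21, and the last two dexamethasone days are Days 22 and 23. Sections 5.1 and 14.7 set the MTD at the dose with fewer than 2 DLTs in 6 subjects. SAP Section 4 defines only the Safety Population and has no DLT-evaluable set.

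**The concern.** A DLT is the event that dose escalation exists to count, so a subject who has one should be informative whatever was taken beforehand. Intake minima are needed only for subjects without a DLT, to show that they were exposed enough for its absence to mean something. Section 5.1.4 follows this logic only up to the last oprozomib dose. After that, the minima apply again to subjects who do have a DLT.

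The MTD is a primary objective and turns on a single event. If a cohort has 2 DLTs in 6 and one of those subjects is replaced by a subject without a DLT, the count becomes 1 in 6 and the dose qualifies. The rule cannot work in the other direction.

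**Working it through.** **1. Days in the DLT window after the last planned oprozomib dose.**
5/14: 28 − 19 = 9 days (9/28 = 32%). 2/7: 28 − 23 = 5 days (5/28 = 18%). The Cycle 2 delay DLT is established only after Day 28 + 14 = Day 42, so it follows the last Cycle 1 oprozomib dose on both schedules.

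**2. Who is affected.** Count the scheduled doses up to the last oprozomib day.

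| Schedule | Pomalidomide | Dexamethasone | Misses that break a minimum if the DLT then stops all drugs |
|---|---|---|---|
| 5/14, to Day 19 | 19 | 6 | 3 pomalidomide (19 − 3 = 16) or 1 dexamethasone (6 − 1 = 5) |
| 2/7, to Day 23 | 21 | 8 | 5 pomalidomide (21 − 5 = 16) or 3 dexamethasone (8 − 3 = 5) |

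A fully dosed subject therefore meets every minimum before a late DLT can occur, and stays evaluable. A subject who missed any oprozomib dose never receives them all, so on the literal wording any DLT in that subject is exempt. The gap needs three things together: all oprozomib taken, a pomalidomide or dexamethasone shortfall, and a DLT after the last oprozomib dose.

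**3. A record that reaches the gap under the protocol's own rules (5/14).** A Grade 3 rash is attributed to pomalidomide. Section 10.5 exempts it as a DLT. Table 14, in its row for other pomalidomide-related toxicity of Grade 3 or higher, keeps oprozomib at full dose and holds pomalidomide. A hold on Days 8–12 leaves 21 − 5 = 16 pomalidomide doses. All 10 oprozomib doses are taken by Day 19. Febrile neutropenia occurs on Day 22. Section 10.5 calls this a DLT. Section 5.1.4 gives no exemption, 16 is below 17, and the subject is to be replaced.

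**4. The fatigue case is conditional.** For "Grade 3 fatigue lasting $< 14$ days", Table 14 keeps oprozomib at full dose and shows a pomalidomide hold. With onset on Day 10, the 14th day is 10 + 13 = Day 23, and 9 of 21 pomalidomide doses have been taken.

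- Dated by the day the 14-day criterion is met, the DLT falls after Day 19 on 5/14, and the subject is unevaluable. On this dating the affected onsets are Days 7–15 on 5/14 and Days 11–15 on 2/7, with 6 to 14 pomalidomide doses taken if the hold continues.
- Dated by onset, all of these precede the last oprozomib dose, and the exemption applies.

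The protocol does not say which date governs.

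**5. Effect on the escalation rule.** Table 18 (Section 14.7; SAP Table 1) follows from

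P(tolerated) = (1 − p)³ + 3p(1 − p)² × (1 − p)³.

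At p = 0.33: 0.301 + 0.444 × 0.301 = 0.434, printed as 0.43. At p = 0.40 it gives 0.309, printed as 0.31. The other four rows also reproduce.

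If a share q of subjects with a DLT is replaced, the counted DLT rate is p′ = p(1 − q)/(1 − pq). The documents give no value for q, so these values are assumptions:

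| q | p = 0.33: p′ | P(tolerated) | p = 0.40: p′ | P(tolerated) |
|---|---|---|---|---|
| 0 | 0.330 | 0.43 | 0.400 | 0.31 |
| 0.03 | 0.323 | 0.45 | 0.393 | 0.32 |
| 0.10 | 0.307 | 0.48 | 0.375 | 0.35 |

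**The case against.** The strongest reply is that the Cohort Safety Review Committee would not let this happen. Section 5.1.3 has every subject discussed and assessed. Section 10.4.1 refers Cycle 1 dose reductions to the committee for evaluability and DLT assessment. Section 10.5 sends non-DLT toxicity that causes a pomalidomide hold to it, which would include the rash above. SAP 7.8 requires its agreement before escalation. The stopping rule in 5.1 speaks of DLTs in a cohort, not of DLTs in evaluable subjects, and SAP 7.6.1 lists all DLTs. Nowhere is it said outright that a replaced subject's DLT is discarded.

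Much of this stands as evidence of intent: DLTs were probably meant always to count, and a careful committee might count them. It does not repair the rule. In 5.1.4 the committee's judgement is a second route to being unevaluable, not a power to waive the minima. Section 10.5 refers only toxicity that is not a DLT. Section 10.4.1 points back to 5.1.4. Being unevaluable for MTD determination, combined with mandatory replacement, implies that the event leaves the count. A committee that kept it would be departing from the text.

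Three stronger readings are tempting, and the documents do not support them. A reader might infer that every late DLT is lost; steps 1 and 2 of the working show that a late DLT alone is not enough. A reader might take 32% and 18% as the share of DLTs lost; they are shares of the calendar, and would be loss rates only if DLT onset were uniform over 28 days and every subject with a late DLT also failed a minimum. A reader might treat every 14-day fatigue DLT with those onsets as dropped; that holds only if the DLT is dated by the day its criterion is met.

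**Conclusion.** The point holds in this limited form. On the literal wording, a subject with all oprozomib taken, fewer than 17 of 21 pomalidomide or 6 of 8 dexamethasone doses, and a DLT after Day 19 (5/14) or Day 23 (2/7) is unevaluable for the MTD and is replaced. The situation can arise when the dose-modification tables are followed, and no other passage overrides 5.1.4.

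That the DLT then drops out of the count is an inference, though a close one. The share of DLTs affected is unknown and probably small. The rise from 0.43 to 0.45 or 0.48 rests on assumed losses of 3% and 10% and is illustrative only.

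It still warrants correction. The rule is wrong as written rather than merely incomplete, it bears on a primary objective, and its error can only favour declaring a dose tolerated. The planned enrolment of about 82 and the 94% response-probability figure are unaffected.

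**What to change.** In 5.1.4 and the synopsis, replace the exemption with a statement that any subject with a DLT as defined in 10.5, including a DLT by Cycle 2 delay, is evaluable and counted regardless of doses received, and that the intake minima apply only to subjects without a DLT. Tie the wording to the 10.5 definition: limiting it to the 4-week evaluation period would leave the Cycle 2 delay DLT uncertain.

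Align Section 12.1, which calls subjects who withdraw before completing Cycle 1 dosing unevaluable and makes no exception for a DLT.

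The protocol's opening note says the programme was terminated and that Amendment 3 was not implemented, so part of the remedy is retrospective. The abbreviated CSR should list the replaced subjects and confirm that none had a DLT. If any did, report the cohort count with that subject included.

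The cost is a sentence in two places, a matching edit in 12.1 and one listing check. The downside is that a few doses may be declared not tolerated that would otherwise have been cleared. No dose or treatment rule changes.

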### **5.1.5 DOSE EXPANSION**

The criteria for selecting the RP3D for 1 or both schedules of oprozomib at the sponsor's discretion will include assessment of the safety, tolerability, and preliminary activity

Approved

observed across multiple cycles of therapy. In addition, both PK and PDn assessments to demonstrate adequate exposure and proteasome inhibition will be a key factor. Therefore, the RP3D may differ from the MTD. Once the MTD and the recommended dose for the expansion phase have been determined, a minimum of 20 additional subjects at 1 or both schedules of oprozomib at the sponsor's discretion will be enrolled in the dose-expansion portion **of the study** in order to continue the evaluation of the safety and efficacy of the regimen. The safety of subjects in the Dose Expansion will be monitored on an ongoing basis by the CSRC during regularly scheduled calls.

## 5.2 ESTIMATED STUDY DURATION AND STUDY CLOSURE

The total study duration is expected to be approximately **12-13** months.

- The Phase 1b portion of the study will take approximately 7–8 months to complete
- Approximately 5 months will be required to enroll and evaluate response status of subjects in the dose-expansion portion of the study

## 5.3 MINIMIZING BIAS

### 5.3.1 BLINDING

Both the dose-escalation and dose-expansion portions of **this study** are open-label.

## 6 SUBJECT SELECTION

### 6.1 INCLUSION CRITERIA

#### Disease Related

2. Multiple myeloma that is primary refractory, relapsed and refractory, or intolerant after at least 2 lines of standard therapy for multiple myeloma, including:
  - a.  $\geq 2$  consecutive cycles of both bortezomib and lenalidomide or thalidomide (alone or in combination)
  - b. In the dose-expansion portion of the study only: In addition to the above, treatment with adequate alkylator therapy, defined as:
    - i. High-dose melphalan or other alkylating agent as conditioning for autologous or allogeneic SCT, or
    - ii.  $\geq 6$  cycles of induction therapy, or
    - iii. Progressive disease after  $\geq 2$  cycles

Approved

3. Measurable disease as indicated by 1 or more of the following:
  - a. Serum M-protein  $\geq$  500 mg/dL
  - b. Urine M-protein  $\geq$  200 mg/24 h
  - c. Only for subjects without measurable M-protein by serum protein electrophoresis (SPEP) and urine protein electrophoresis (UPEP), involved free light chain (FLC) concentration  $\geq$  10 mg/dL provided serum free light chain (SFLC) ratio is abnormal
4. Disease progression on or within 60 days of completion of the last therapy, or intolerance to bortezomib if received as their last therapy
  - a. Patients who received bortezomib as their last therapy who were not refractory but developed bortezomib intolerance, as defined by the development of Grade 2 peripheral neuropathy with pain or  $\geq$  Grade 3 peripheral neuropathy after  $\geq$  2 consecutive cycles, are eligible
5. Prior carfilzomib is allowed if a subject was not removed from carfilzomib therapy due to toxicity, unless approved by the **Sponsor's** study medical monitor.

#### Demographic

6. Males and females  $\geq$  18 years old
7. Eastern Cooperative Oncology Group (ECOG) Performance Status of 0–2 ([Appendix H](#))

#### Laboratory

8. Adequate hepatic function, with bilirubin  $\leq$  1.5 times the upper limit of normal (ULN) in the absence of Gilbert's disease or hemolysis, and alanine aminotransferase (ALT) and aspartate aminotransferase (AST)  $\leq$  3 times ULN
9. Absolute neutrophil count (ANC)  $\geq$  1500/mm^3. Screening ANC should be independent of myeloid growth factor support for at least 1 week or 2 weeks for pegylated growth factors.
10. Hemoglobin  $\geq$  8.0 g/dL. Patients may receive red blood cell (RBC) transfusions or receive erythropoietin or darbepoetin alfa in accordance with institutional guidelines up to 1 week before screening.
11. Platelet count  $\geq$  75,000 mm^3. Patients should not have received platelet transfusions for at least 1 week before screening.
12. Uric acid, if elevated, must be corrected to within laboratory normal range before dosing.
13. Calculated or measured creatinine clearance (CrCl)  $\geq$  30 mL/min calculated using the formula of Cockcroft and Gault [(140 – age)  $\times$  mass (kg) / (72  $\times$  serum creatinine mg/dL)]. Multiply result by 0.85 if female.

Approved

### Ethical/Other

14. Patient must sign a written informed consent form in accordance with federal, local, and institutional guidelines.
15. Female patients of childbearing potential must have a negative pregnancy test (with a sensitivity of at least 50 mIU/mL) within 1 day of the first dose of study drug and agree to use 2 effective methods of contraception during the study and for 28 days following the last dose of study drug. Postmenopausal females (> 45 years old and without menses for  $\geq 2$  years) and surgically sterilized females are exempt from these requirements.
16. Male patients, including those with prior vasectomy, must use an effective barrier method of contraception during the study and for 3 months following the last dose if sexually active with a female of childbearing potential. Additionally, they must agree not to donate sperm while being treated and for up to 3 months after discontinuing treatment.

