### 10.6.1 REQUIRED CONCOMITANT MEDICATIONS

#### 10.6.1.1 Contraception

Females of reproductive potential must commit either to abstain continuously from heterosexual sexual intercourse or to use 2 methods of effective contraception simultaneously (1 highly effective form of contraception—tubal ligation, intrauterine device [IUD], hormonal [birth control pills, injections, hormonal patches, vaginal rings or implants] or partner's vasectomy and 1 additional effective contraceptive method—male latex or synthetic condom, diaphragm, or cervical cap). Contraception must begin 4 weeks prior to initiating treatment and continue during therapy, dose interruptions, and for 28 days after discontinuation of therapy. Reliable contraception is indicated even where there has been

Approved

CONFIDENTIAL

a history of infertility, unless this is due to hysterectomy. Females of reproductive potential should be referred to a qualified provider of contraceptive methods, if needed. Additional details are provided in Pomalidomide Risks of Fetal Exposure, Pregnancy Testing Guidelines and Acceptable Birth Control Methods ([Appendix J](#)), Pomalidomide Education and Counseling Guidance Document ([Appendix K](#)), and Pomalidomide Information Sheet for Subjects Enrolled in Clinical Research Studies ([Appendix L](#)).

Females of reproductive potential must have 2 negative pregnancy tests before initiating study treatment. The first test should be performed within 10–14 days of study treatment and the second test should be performed within 24 hours before study treatment. Once treatment has started and during dose interruptions, pregnancy testing for female subjects of reproductive potential should occur weekly during the first 4 weeks of treatment. Pregnancy testing should be repeated every 4 weeks thereafter for female subjects with regular menstrual cycles. For female subjects with irregular menstrual cycles ( $\pm 7$  days of a 28-day cycle), pregnancy testing should be performed every 2 weeks. Pregnancy testing and counseling should be performed if a subject misses her period or if there is any abnormality in her menstrual bleeding. Study treatment must be discontinued during this evaluation.

Postmenopausal females ( $> 45$  years old and without menses for  $> 2$  years) and surgically sterilized females are exempt.

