**APPENDIX A1 SCHEDULE OF STUDY ASSESSMENTS – PHASE 1B DOSE ESCALATION 5/14 SCHEDULE (CONT'D)**

-  Coagulation tests, done locally **if clinically indicated**, and includes the following: Prothrombin time, activated partial thromboplastin time, and international normalized ratio.
- m Screening pregnancy testing, done locally, for females of childbearing potential (FCBP) must have a sensitivity of at least 50 mIU/mL with TWO medically supervised tests performed before pomalidomide dosing starts. One test must be obtained within 10–14 days and one test within 24 hours prior to the start of pomalidomide on Cycle 1 Day 1. A medically supervised, serum pregnancy test will be done weekly during Cycle 1 (Days 1, 8, 15, and 22). Starting with Cycle 2, serum pregnancy tests will be done within 24 hours prior to each cycle of pomalidomide dosing in FCBP only. Pregnancy tests will be repeated on Day 15 of Cycle 2 and beyond if menses are irregular (i.e., not within  $\pm 7$  days of a 28-day cycle) or menses are not present in FCBP.
- n Results for SPEP, UPEP, and SFLC, obtained locally, during Screening must be available before starting study drug treatment. When the subject is on study drug, the disease response assessments will be performed at the end of each cycle (Day 22–28 or prior to dosing on Day 1 of the next cycle) for the first 18 months (Cycles 1–18), then every 8 weeks thereafter (starting with Cycle 20). If the subject comes off study for reasons other than progressive disease, then disease response assessments will be performed every 4 weeks through 18 months on study, and then every 8 weeks thereafter. Obtain blood for SPEP (please refer to [Section 11.3](#) for collection times for SPEP Immunofixation, UPEP and UPEP Immunofixation with 24-hr urine, and sFLC) within 7 days prior to next Cycle study drug dosing. If a response assessment indicates PD, confirmation of PD may be obtained any time at or before the next scheduled assessment.

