### Criteria for Females of Childbearing Potential (FCBP)

This protocol defines a female of childbearing potential as a sexually mature woman who: 1) has not undergone a hysterectomy or bilateral oophorectomy or 2) has not been naturally postmenopausal (amenorrhea following cancer therapy does not rule out childbearing potential) for at least 24 consecutive months (i.e., has had menses at any time in the preceding 24 consecutive months).

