**Contraception**

Females of childbearing potential enrolled in this protocol must agree to use 2 reliable forms of contraception simultaneously or to practice complete abstinence from heterosexual intercourse during the following time periods related to this study: 1) for at least 28 days before starting study drug; 2) while participating in the study; 3) dose interruptions; and 4) for at least 28 days after study treatment discontinuation.

The 2 methods of reliable contraception must include 1 highly effective method and 1 additional effective (barrier) method. An FCBP must be referred to a qualified provider of contraceptive methods if needed.

Approved

The following are examples of highly effective and additional effective methods of contraception:

- Highly effective methods:
  - Intrauterine device (IUD)
  - Hormonal (birth control pills, injections, implants)
  - Tubal ligation
  - Partner's vasectomy
- Additional effective methods:
  - Male condom
  - Diaphragm
  - Cervical cap

Because of the increased risk of venous thromboembolism in patients with multiple myeloma taking pomalidomide and dexamethasone, combined oral contraceptive pills are not recommended. If a subject is currently using combined oral contraception the subject should switch to another one of the effective methods listed above. The risk of venous thromboembolism continues for 4–6 weeks after discontinuing combined oral contraception.

The efficacy of contraceptive steroids may be reduced during co-treatment with dexamethasone.

Implants and levonorgestrel-releasing intrauterine systems are associated with an increased risk of infection at the time of insertion and irregular vaginal bleeding. Prophylactic antibiotics should be considered, particularly in subjects with neutropenia.

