**Before starting study drug**

***Female Subjects***

Females of childbearing potential must have 2 negative pregnancy tests (sensitivity of at least 50 mIU/mL) prior to starting pomalidomide. The first pregnancy test must be performed within 10-14 days prior to the start of pomalidomide and the second pregnancy test must be performed within 24 hours prior to the start of pomalidomide. The subject may not receive study drug until the investigator has verified that the results of these pregnancy tests are negative.

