**During study participation and for 28 days following study drug discontinuation**

***Female Subjects***

- Females of childbearing potential with regular or no menstrual cycles must agree to have pregnancy tests weekly for the first 28 days of study participation and then every 28 days while on study, at study discontinuation, and at Day 28 following study drug discontinuation. If menstrual cycles are irregular, the pregnancy testing must occur weekly for the first 28 days and then every 14 days while on study, at study discontinuation, and at Days 14 and 28 following study drug discontinuation.
- At each visit, the investigator must confirm with the FCBP that she is continuing to use 2 reliable methods of birth control.
- Counseling about pregnancy precautions and the potential risks of fetal exposure must be conducted at a minimum of every 28 days.
- If pregnancy or a positive pregnancy test does occur in a study subject, pomalidomide must be immediately discontinued.
- Pregnancy testing and counseling must be performed if a subject misses her period or if her pregnancy test or her menstrual bleeding is abnormal. Study drug treatment must be discontinued during this evaluation.
- Females must agree to abstain from breastfeeding during study participation and for at least 28 days after study drug discontinuation.

Approved

Onyx Therapeutics  
Oprozomib ER Tablets

Clinical Study Protocol No. OPZ007  
Page 142 of 223

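### The eligibility exemption from pregnancy testing and contraception is wider than the definition of childbearing potential in Appendices I and J, so two groups of women can start pomalidomide untested

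*Protocol*

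**What the plan says.** **Eligibility and body text.** Criterion 15 of Protocol Section 6.1 requires a negative pregnancy test within 1 day of first dose and two contraceptive methods. It then exempts two groups. One is postmenopausal women, described only by age over 45 and at least 2 years without menses. The other is women sterilized surgically: "surgically sterilized females are exempt from these requirements". Synopsis criterion 14 is the same. Section 10.6.1.1 ends with the same exemption ("surgically sterilized females are exempt"), but with more than 2 years in place of at least 2.

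**Section 10.6.1.1 on tubal ligation.** The same section names tubal ligation among the methods a woman of reproductive potential may use: "1 highly effective form of contraception—tubal ligation, intrauterine device [IUD". It also keeps contraception in force for a woman with a history of infertility, unless a hysterectomy is the cause.

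**Appendix I** gives what it presents as the protocol's own definition. A woman stops being of childbearing potential after a hysterectomy, after removal of both ovaries, or once naturally postmenopausal for 24 months, and "amenorrhea following cancer therapy does not rule out childbearing potential". Women of childbearing potential need contraception "for at least 28 days before starting study drug" and two tests before treatment: "The first pregnancy test must be performed within 10-14 days prior to the start of pomalidomide", then a second within 24 hours of the start. Testing continues on treatment, including for those without periods: "Females of childbearing potential with regular or no menstrual cycles must agree to have pregnancy tests weekly for the first 28 days". Footnote m of the assessment schedules agrees: "A medically supervised, serum pregnancy test will be done weekly during Cycle 1 (Days 1, 8, 15, and 22".

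**Appendix J**, the form completed before each dispensing, prints the same definition and a closed list of who is not of childbearing potential. Tubal ligation is not on that list. The form forbids dispensing to a woman of childbearing potential who has not been tested.

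**The concern.** Two rules for the same decision give different answers, and the looser one is the rule a site applies at screening. Criterion 15 supplies its own test for exemption and does not point to the Appendix I definition.

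The drug is a thalidomide analogue, and Appendix I describes thalidomide as a known human teratogen. The population makes the amenorrhea group foreseeable. Every subject has had at least two prior lines of therapy. The expansion part also requires alkylator exposure, which can include high-dose melphalan as transplant conditioning.

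If a site follows criterion 15 as written, a woman in either group is enrolled with no pregnancy test and no contraceptive lead-in. If that classification is carried onto the Appendix J form, she is dosed untested. A woman with a tubal ligation would then have one of the two required methods and no barrier.

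**Working it through.** No power, rate or sample-size calculation is involved. The check is to classify the two groups under each page, then count what each page requires.

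**Step 1. Classification**

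| Place | Tubal ligation, not otherwise exempt | Over 45, at least 2 years of amenorrhea after cancer therapy |
|---|---|---|
| Section 6.1 criterion 15; synopsis criterion 14 | Exempt, if surgical sterilization has its ordinary meaning | Exempt: meets the age and menses test; no cause is asked for |
| Section 10.6.1.1, exemption sentence | Exempt, same reading | Exempt once past 2 years |
| Section 10.6.1.1, list of methods | Treated as needing contraception; the ligation counts as one method | Not addressed |
| Appendix I | Of childbearing potential: only removal of the uterus or both ovaries counts surgically | Of childbearing potential: menopause is not natural |
| Appendix J | Of childbearing potential: not on the closed list | Of childbearing potential: not on the closed list |

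Neither appendix states in one sentence that a woman with a tubal ligation is of childbearing potential. That follows from three things together: the surgical limb of the definition, the closed list, and the listing of tubal ligation as a method for such women. If ligation were enough for exemption, the listing would serve no purpose.

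**Step 2. Tests required through the end of Cycle 1** (Appendix I and schedule footnote m)

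- Before treatment: 1 test at 10–14 days + 1 test within 24 hours = 2.
- On treatment, taking the 24-hour test as the Day 1 test: Days 8, 15 and 22 = 3.
- Total: 2 + 3 = 5. If Day 1 needs its own test: 5 + 1 = 6.
- Under the criterion 15 exemption: 0.

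**Step 3. Delay if the status is corrected only on the dispensing day**

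- The first test must precede pomalidomide by 10–14 days, so the wait is at least 10 days.
- Contraception must precede it by 28 days, so the wait is up to 28 days if two methods were not already in use.
- Section 7 requires screening to be completed within 28 days of first dose. The upper end of the delay is as long as the whole window (28 against 28).

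**The case against.** The strongest reply is that the terms can be read together. Criterion 15 opens by referring to women of childbearing potential, and Appendix I says its definition is the protocol's. Section 10.6.1.1 lists tubal ligation as a method and accepts only hysterectomy as a reason for infertility to end contraception. On that reading, surgical sterilization means hysterectomy or oophorectomy, postmenopausal means naturally so, and the conflict disappears. This has some force for tubal ligation, where the broad reading rests on the ordinary meaning of an undefined term. It fails for amenorrhea: criterion 15 spells out its own age-and-menses test, and a woman with therapy-related amenorrhea meets it.

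The second reply is that there are other safeguards: counselling before treatment, the investigator's duty to verify both negative tests, the screening pregnancy test in the schedule, the medical monitor's review before enrollment, and the Appendix J form. Appendix J should indeed catch many cases, and a delay before dosing is that safeguard working. But the counselling on contraception, the verification and the tests apply in full only once a woman has been classed as of childbearing potential, which is the step in dispute. The monitor's review is not tied to either definition.

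Three further points stand. Few women are likely to be affected. The appendix letters cited in Section 10.6.1.1 are off by one, but that is clerical because the full titles are printed beside them. Amendment 3 was approved but not implemented before the program was terminated, so corrected entry criteria would reach no new subject here. The value now lies in reuse of the wording; the termination does not make the text consistent.

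**Conclusion.** The concern holds. Followed as written, criterion 15, synopsis criterion 14 and the closing exemption in Section 10.6.1.1 release women whom Appendices I and J require to be tested and to use two methods of contraception. Two groups change status between pages, and for each the requirement through the end of Cycle 1 is 0 tests or 5 (6 if Day 1 is separate). The conclusion is firm for women over 45 with long therapy-related amenorrhea. For tubal ligation it assumes the ordinary meaning of surgical sterilization. The number of women is not given in the documents and is probably small. The possible harm, fetal exposure to a thalidomide analogue, is severe and irreversible. This should be fixed; it affects no endpoint or analysis.

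**What to change.** 1. In criterion 15, synopsis criterion 14 and Section 10.6.1.1, replace the exemption sentence with the Appendix I definition, worded as the Appendix J closed list: hysterectomy, removal of both ovaries, or natural menopause of at least 24 months. State that tubal ligation and amenorrhea after cancer therapy do not exempt.
2. Add a cross-reference from criterion 15 to the two pre-treatment tests and the 28-day contraception lead-in in Appendix I.
3. Have the medical monitor's pre-enrollment review in Section 8 record childbearing status from this definition, so that it is settled at screening and not at dispensing.
4. Correct the appendix letters cited in Section 10.6.1.1 at the same time.

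The cost is a wording change in an amendment, plus a few pregnancy tests and barrier-method use in a small subgroup.
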